## Sex Effects on Blood Pressure With Handgrip Training

### Research protocol

This study will be designed as a randomized, controlled, cross-over, repeated measures experiment. Fifty young healthy adult participants (25 males and 25 females) will visit the laboratory three times to perform a fatiguing bout of isometric handgrip exercise before and after both 4 weeks of isometric handgrip training and a no-exercise training condition. Participants will be randomly allocated to the isometric handgrip and the non-exercise training conditions using an online program (<http://www.randomizer.org/>). Participants that start with isometric handgrip training will return to the laboratory after a 4-wk washout, as this duration has been shown to decondition cardiovascular outcomes following training (1–3). To eliminate diurnal variation, each participant will visit the laboratory at the same time of day. Main outcomes in each visit will be measured at rest, during the fatiguing bout of isometric handgrip exercise, and 5, 10, 30, and 60-min post-exercise (see figure and Table 1). These measurement timings are aimed to characterize BP, and the cardiac autonomic and vascular function biphasic responses (4–6). Visits 2 and 3 will take place within 7 days of the last training session.

**Figure 1:** Experimental design, a randomized, controlled, cross-over, repeated measurements study. Abbreviations: CON; control, BRS baroreflex sensitivity, RMSSD, root mean square of

**Table 1** Procedures to be conducted in each visit to the laboratory

Procedures	Time (min)
Rest	15
Measurements	
1) BP, arterial stiffness, cardiac autonomic function	5
2) Brachial endothelial function (FMD)	15
Fatiguing isometric handgrip exercise	~ 3-5
Last isometric contraction	
Measurements	
1) BP, brachial blood flow	
2) Cardiac autonomic function (BRS, RMSSD, HF)	
Post 5 min	
Measurements	
1) BP, arterial stiffness (cfPWV), cardiac autonomic function (BRS, RMSSD, HF)	5
Post 10 min	
Measurements	
1) Brachial endothelial function (FMD)	15
Post 30 min	
Measurements	
1) BP, arterial stiffness (cfPWV), cardiac autonomic function (BRS, RMSSD, HF)	5
2) Brachial endothelial function (FMD)	15
Post 60 min	
Measurements	
1) BP, arterial stiffness (cfPWV), cardiac autonomic function	5
2) Brachial endothelial function (FMD)	15
	Total ~ 100

successive differences; HF, high-frequency power band; FMD; brachial artery flow-mediated dilation, cfPWV; central pulse wave velocity.

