### Sample size

Based upon an effect size of 0.160 and a drop-out rate of 15%, a priori power analysis (G-Power Version 3.1.9.3) for mixed ANOVA suggested a total of 50 participants are required to detect SBP mean differences of at least 5 mmHg over time and groups ( $\alpha = 0.05$ ,  $1-\beta=0.80$ ). Despite this mean difference obtained from a study that characterized BP responses after acute isometric handgrip exercise (7), we also aim to examine the effects of training on acute blood pressure responses to isometric handgrip exercise. Thus, given these differences in study design, we additionally set the effect size considering the small, standardized effect sizes ( $\leq 0.20$ ) for exercise training sciences (31).

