### Statistical analysis

Linear mixed models will be used to examine the effects of acute isometric handgrip exercise and training on BP, cardiac autonomic, and vascular function outcomes over time (i.e., aim 1, 2, and 3). These will be fitted with restricted maximum likelihood and applying Satterthwaite's method for approximating degrees of freedom for the F test using R lmerTest package (32). Fixed effects will be set as time, sex, training condition, and the random intercept as each participant. All models' residuals will be checked for normality and homogeneity of

variances using both Shapiro-Wilk and Levene tests, respectively, and through QQ plot inspection using the R performance package (33). Natural logarithm (Ln) transformations will be applied to HRV outcomes, as these are generally not normally distributed, but both transformed and untransformed data will be presented. Linear mixed models will be run with and without possible outliers identified through box plots as observations lying outside the 1.5 interquartile range. Unbiased effect sizes - partial omega squares ( $\omega^2$ ) will be estimated for each fixed effect and interactions terms and interpreted accordingly to the rough benchmarks set by Cohen (34) [small ( $\omega^2 < 0.05$ ), medium ( $\omega^2 < 0.25$ ), and large ( $\omega^2 > 0.25$ ) effects sizes]. Post-hoc comparisons will be performed using the Bonferroni correction, in the presence of significant fixed effects and interactions. MVC, %fat and free fat mass, and physical activity outcomes will be added to all linear mixed models as covariates, whereas resting HR and SRauc will be added to FMD and HRV main outcomes, respectively. In addition, the repeated measures correlation coefficient will be used to test associations between isometric handgrip exercise-induced BP changes before and after the training intervention and of BP with cardiac autonomic and vascular function outcomes (35). Multiple imputation procedures using full information maximum likelihood will only be used in case of a significant amount of missing data on outcomes (>15%) and if missing completely at random, as linear mixed modeling provides robust estimates for small to medium amounts of missingness (36). All statistical analyses will be conducted using R software, version 4.2.3 (37) with a significant level ( $\alpha$ ) of 0.05.

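### With a participant intercept as the only random effect, acute responses repeated at three visits count as independent, so the sex-by-time test can be anti-conservative

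*Combined protocol and SAP*

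**What the plan says.** The Research protocol section has participants who "will visit the laboratory three times to perform a fatiguing bout of isometric handgrip exercise", and the Study intervention sections confirm that the bout is the same each time. Table 1 places BP and autonomic readings at rest, at the last contraction, and at 5, 30 and 60 minutes. FMD and cfPWV have four time points and none during contraction. Under Blood pressure, the brachial cuff is used only before and after exercise; readings during exercise come from the finger device.

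Under Statistical analysis the model is "Fixed effects will be set as time, sex, training condition, and the random intercept as each participant", fitted by REML with Satterthwaite's method "for approximating degrees of freedom for the F test using R lmerTest package". Effect sizes "will be estimated for each fixed effect and interactions terms", so interactions are in the model, although sex-by-time is not named. Bonferroni post-hoc comparisons follow significant effects. No random slope, participant-by-time or participant-by-visit term, residual correlation structure or robust variance appears anywhere.

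**The concern.** A person who reacts strongly to the bout will tend to do so at each visit. Averaging three visits does not remove that tendency, but the model treats it as residual noise and divides it by three. Sex is a between-person factor, so the information about a sex difference in the response is one value per person, not three.

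The trial is titled as a study of sex effects, so a sex difference in the acute response is a natural headline result. The plan's diagnostics (Shapiro-Wilk, Levene, QQ plots) do not look at residual correlation and would not reveal the problem. The plan also intends to correlate exercise-induced BP changes before and after training, so it already expects acute responses to be linked across visits.

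**Working it through.** **1. The plan's own figure.** The Sample size section works from "Based upon an effect size of 0.160 and a drop-out rate of 15"%, for "SBP mean differences of at least 5 mmHg over time and groups", with alpha 0.05 and power 0.80; it says G-Power "for mixed ANOVA suggested a total of 50 participants are required". I read 0.160 as Cohen's f and test the within-between interaction with λ = f²Nm/(1−ρ), df1 = m−1 and df2 = (N−2)(m−1). Assuming ρ = 0.5:
- m = 6 gives 44, and 44/0.85 = 51.8, so 52 (44 × 1.15 = 50.6, so 51). This is close to 50.
- m = 5, the number of BP time points, gives 48, and 48/0.85 = 56.5, so 57.

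Neither m nor ρ is stated, nor any SD or variance component, so the calculation cannot settle the size of the problem. I analyse 42 participants (50 × 0.85 = 42.5), 21 per sex.

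**2. Where the error term goes wrong.** Take 3 visits, 5 time points, saturated sex × visit × time means and residual variance 1. Let τ² be the participant-by-time variance, equal at all times, and φ² the participant-by-visit variance. Each participant has 14 within-person df.
- E[MS sex-by-time] = 1 + 3τ²
- E[MS residual] = 1 + (4·3τ² + 2·5φ²)/14 = 1 + 0.857τ² + 0.714φ²

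The test is inflated when φ² < 3τ². It uses 40 × 14 = 560 denominator df instead of 40 × 4 = 160. With one visit and equal τ² it holds 5%, so the repetition over visits is the cause. Over the grid τ² = 0 to 2, φ² = 0 to 1, the rejection rate runs from under 1% to about 45%.

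**3. Exercise minus rest, in mmHg.** Assume residual SD σ = 6, response SD ω at the exercise reading only, and visit SD ν.
- True variance of a participant's mean change over three visits: ω² + 2σ²/3 = ω² + 24
- Variance the model uses: 2s²/3, with s² = σ² + [3(1 − 1/5)ω² + 10ν²]/14 = 36 + 0.171ω² + 0.714ν²
- r = √(model/true); type I error ≈ 2Φ(−1.964r)

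| ν | ω | s² | model | true | r | type I |
|---|---|---|---|---|---|---|
| 0 | 4 | 38.7 | 25.8 | 40 | 0.80 | 12% |
| 0 | 8 | 47.0 | 31.3 | 88 | 0.60 | 24% |
| 0 | 12 | 60.7 | 40.5 | 168 | 0.49 | 34% |
| 4 | 4 | 50.2 | 33.4 | 40 | 0.91 | 7% |
| 4 | 8 | 58.4 | 38.9 | 88 | 0.67 | 19% |
| 4 | 12 | 72.1 | 48.1 | 168 | 0.53 | 29% |
| 6 | 4 | 64.5 | 43.0 | 40 | 1.04 | 4% |
| 6 | 8 | 72.7 | 48.5 | 88 | 0.74 | 14% |
| 6 | 12 | 86.4 | 57.6 | 168 | 0.59 | 25% |

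Simulation gives 12/24/34%, 8/19/31% and 5/14/26%, within two points of the formula. The omnibus sex-by-time F runs at about 9-29%, 4-23% and 2-18% for the three visit SDs. A test on one mean change per participant stays at 4-6%.

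**4. Adding only a visit term.** The residual then has 12 df per person and s² = 36 + 0.2ω², whatever the visit SD. The same formula gives 11%, 23% and 32% for ω = 4, 8 and 12. The offset from visit variance is gone and the inflation is back.

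**5. Recovery contrasts.** Let the individual deviation have SD ω at every post-rest time, independently. With five times, s² = 36 + 0.686ω² + 0.714ν². For ω = 4 and 6 this gives 8% and 11% at ν = 0, 5% and 8% at ν = 4, and 3% and 5% at ν = 6. Four time points change these by less than one percentage point. The omnibus F is more exposed: with four times and ν = 4 it is about 10-21%.

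**6. Training-by-time.** For exercise minus rest compared between two visits, the true per-participant variance is 4σ² and the model uses 4s². This assumes that the individual response does not itself change between visits. The standard error is too large by the factor s/σ: 4-30% at ν = 0, 18-42% at ν = 4 and 34-55% at ν = 6.

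**The case against.** The strongest reply is that no false-positive rate can be read from the documents, because they give no residual, visit or response SD. That stands. A reader might infer that the plan simply has a 10-30% error rate for sex-by-time. The documents do not support this. Such a range comes from assumed variances, and its lower end disappears once ordinary visit-to-visit variation is allowed for: at a response SD of 4 and a visit SD of 6 the rate is about nominal. The two omissions partly cancel in the model as written.

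A second reply is that the planned procedure is an F test followed by Bonferroni comparisons, not one uncorrected contrast. This also stands. If a significant F is required and Bonferroni is taken over four change-from-rest contrasts (an assumption, since the family is not defined), exercise minus rest is declared in about 3%, 12% and 20% of null trials at visit SD 0, and 1.5%, 8% and 16% at visit SD 4. Protection is partial at the larger response SDs.

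Third, cuff BP, FMD and cfPWV have no reading during exercise, so the largest figures do not apply to them. For FMD and cfPWV even the recovery figures carry over only as ratios of response SD to residual SD.

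Finally, sex-by-time is not named as the key test, and questions about training rest on within-person contrasts, where the error is lost precision rather than false positives. None of this supplies the missing variance term. The offset from visit variance is accidental and goes as soon as a visit term is added.

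**Conclusion.** The specification gap is real. One participant intercept cannot represent individual acute responses that recur over three visits, so sex-by-time can be anti-conservative and training-by-time is tested with standard errors that are too large. The direction for sex-by-time is conditional: in the equal-variance case the test is inflated when the participant-by-visit variance is less than three times the participant-by-time variance, and otherwise sits at or below 5%.

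The brief's figures for exercise minus rest and for recovery are illustrations. They assume 42 participants with complete data, a residual SD of 6 mmHg and the stated response and visit SDs. They are not properties of the trial. For outcomes without a reading during exercise, only the recovery contrasts and the omnibus F are at issue, and the F can still be clearly inflated.

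**What to change.** In Statistical analysis, specify participant-by-visit and participant-by-time random effects together, and give the during-exercise time point its own variance where it is measured. The separate variance matters: if individual variation sits mainly at exercise, an equal-variance participant-by-time term leaves about 5-10%.

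Name a fallback in case the model does not converge: for each sex-by-response contrast, compute one mean change per participant (time t minus rest, averaged over visits) and compare the sexes on between-participant df. That is the number of participants minus 2, less any covariates; for example 42 − 2 = 40 before covariates. State how participants with fewer than three visits are handled.

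The cost is a few lines of SAP and model code, with no new data. Intervals for sex-by-time will be wider, and convergence problems are possible with this many variance terms.

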#### *Blood pressure*

Participants will be asked to wear a non-invasive inflating and deflating finger cuff during all study visits. This will allow beat-to-beat BP to be recorded using finger plethysmography (Finometer; Finapres Medical System, Amsterdam, The Netherlands) before, during, and after isometric handgrip exercise in the supine position. Beat-to-beat BP will be averaged offline over 2 to 5-min using Lab Chart 8 (ADIInstruments, BellaVista, NSW, Australia). Beat-to-beat dynamic fluctuations in BP induced by acute isometric handgrip exercise will be quantified through BP variability indices including spectral methods using the adapted HRV module of Lab Chart 8. This will give insight into sympathetic outflow to blood vessels (14,15).

**Brachial BP** of the right arm will also be measured three times at 1-minute intervals before and after isometric handgrip exercise using an automated blood pressure cuff (HEM-7311-ZSA; Omron Healthcare Co, Ltd, Kyoto, Japan) (16). Measurements will be accepted if they do not differ > 4 mmHg, and the average of the last two will be used for data analysis (16). Mean arterial pressure will be estimated as  $2/3 \text{ DBP} + 1/3 \text{ SBP}$ .

**Central BP** will be assessed via carotid artery tonometry (NIHem, Cardiovascular Engineering Inc., Norwood, MA). Brachial systolic and diastolic cuff BPs will be used to calibrate the peak and trough of the signal-averaged pressure waveforms. Carotid pressure waveforms will be calibrated with diastolic and integrated mean brachial cuff pressure. Central BP is then estimated from the calibrated carotid pressure. Central pulse pressure will be calculated as the difference between the peak and trough of the calibrated carotid pressure waveform.

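### The outlier rule uses a box plot of observations, not tied to the fitted mixed model, and the plan does not say whether the full or the trimmed run carries the conclusion

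*Combined protocol and SAP*

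**What the plan says.** The rule is one sentence under Statistical analysis: "Linear mixed models will be run with and without possible outliers identified through box plots as observations lying outside the 1.5 interquartile range". The model it applies to is described just before: "Fixed effects will be set as time, sex, training condition, and the random intercept as each participant". Residuals appear in that section only for assumption checking, where the models' "residuals will be checked for normality and homogeneity of" variance. They are not mentioned in connection with outliers. For scale, "Natural logarithm (Ln) transformations will be applied to HRV outcomes", with untransformed data also presented.

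The data are repeated measures across very different physiological states. The design section states: "Fifty young healthy adult participants (25 males and 25 females) will visit the laboratory three times". The Blood pressure section has beat-to-beat pressure recorded "before, during, and after isometric handgrip exercise in the supine position". Table 1 lists blood pressure at five times per visit: rest, last contraction, and 5, 30 and 60 minutes afterwards.

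The plan does not say:
- whether the box plot is pooled over times or drawn within cells;
- whether HRV is screened on the log or the original scale;
- which run is reported as the result, or what follows if the two disagree;
- whether a flagged value is checked for measurement error before it is left out.

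**The concern.** A box plot of observations asks whether a value is far from the middle of all the values plotted. A mixed model asks whether it is far from what is expected for that person at that time. Here the two questions differ. A reading taken at the end of a contraction held to task failure is meant to be high, and the acute response is one of the effects to be estimated. A pooled box plot can treat that response as an anomaly. A box plot within each sex, visit and time avoids this, but it still ignores the participant's own level and trims ordinary tails, especially in small cells.

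At stake is the meaning of the trimmed run. If it disagrees with the full run, the reader cannot tell whether a few faulty readings drove the result or whether the rule removed real responses. Because no run is designated as the main one, that ambiguity could carry into the conclusion for each of the seven main outcomes (SBP, DBP, RMSSD, HF, baroreflex sensitivity, FMD, cfPWV).

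**Working it through.** The plan gives no figure for the outlier rule, so there is nothing of its own to reproduce.

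**Inputs from the documents.** 50 participants, 25 per sex; three visits; five blood pressure times, so up to 50 × 3 × 5 = 750 observations. With the planned 15% drop-out, 50 × 0.85 = 42.5, taken as 42 (21 per sex), giving 42 × 3 × 5 = 630.

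**Inputs assumed.** The documents give no SD and no exercise rise. Assumed: SBP 115 mmHg (SD 9) at non-exercise times; exercise rise 20-50 mmHg with SD 12-18; within-person correlation 0.5 unless stated.

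**Reading A: one pooled box plot.** Exercise readings are one fifth of the data. The quartiles solve 0.8 Φ((x − 115)/9) + 0.2 Φ((x − 115 − rise)/SD) = 0.25 and 0.75. The upper fence is Q3 + 1.5 (Q3 − Q1).
- Rise 20, SD 12: Q1 = 110.5, Q3 = 125.7, fence = 125.7 + 1.5 × 15.2 = 148.5. Share of exercise readings above it: 1 − Φ((148.5 − 135)/12) = 1 − Φ(1.125) = 13%.
- Rise 50, SD 12: Q1 = 110.6, Q3 = 128.8, fence = 128.8 + 1.5 × 18.2 = 156.1. Share above it: 1 − Φ((156.1 − 165)/12) = 1 − Φ(−0.74) = 77%.

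Simulation with 42 participants over the whole assumed range gives 14-77% of exercise readings flagged, against about 0.2% or fewer of the others. Removing them lowers mean exercise SBP by 3-22 mmHg. For scale, the Sample size section targets an SBP difference of 5 mmHg. An assumed true sex difference of 10 mmHg in exercise SBP becomes about 2-6.5 mmHg, because the sex with the larger response loses more readings. These are changes in simple means, not mixed-model estimates.

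**Sensitivity of Reading A.** With exercise SD held at 9, the flagged share is 5-83%. With equal spread at all times and 750 observations:

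| Exercise shift (within-cell SD) | Exercise readings flagged | Fall in exercise-minus-rest difference |
|---|---|---|
| 1 | 1.9% | 0.05 SD |
| 2 | 4.4% | 0.10 SD |
| 3 | 10.7% | 0.20 SD |
| 4 | 32% | 0.52 SD |

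At a shift of 3 SD, 16.0 of the 16.3 values flagged on average are exercise values. The direction is stable; the size depends on the assumptions.

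**Reading B: a box plot per sex, visit and time.** For a large normal sample the fence is 0.6745 + 1.5 × 1.349 = 2.70 SD, and 2(1 − Φ(2.70)) = 0.70% is flagged. Small cells flag more because their quartiles are noisy: about 2.5% at n = 21 (0.025 × 630 ≈ 16 readings) and about 2.1% at n = 25 (0.021 × 750 ≈ 16), where a clean cell has a 33% chance of losing at least one value. The SD within a cell of 21 falls by about 7%. The quantity that matters for within-person contrasts is the mixed model's residual SD. With an assumed within-person correlation of 0.6, it falls by about 2.5% if the exercise rise is uniform and about 4-4.5% if it varies between people.

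**Scale.** If skewed outcomes were screened before log transformation, lognormal data with log SD 0.4 to 0.8 would have 3.0-6.4% of values flagged with nothing wrong.

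**Residuals instead.** The same 1.5 IQR fence applied to residuals (visit-by-time and person means removed, equal spread at each time) flags about 0.7% at the exercise time and about 0.7% elsewhere, whatever the shift: about 5.5 of 750. The concentration on exercise readings disappears, but some trimming of normal tails remains.

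**The case against.** The strongest reply is that nothing is lost. The all-data model is always fitted, the values are called only possible outliers, and comparing two runs is an ordinary sensitivity check. That stands. A reader might infer that the plan deletes genuine exercise responses from its analysis, or that it sets up a choice of the more favourable result for each outcome. The text supports neither: running both can equally mean reporting both.

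A reader might also infer that the plan screens raw values pooled over all times. It says observations and stops there. Raw values are the natural reading, since residuals are named separately for other purposes, but pooling is neither stated nor excluded. The 14-77% figure therefore depends on one reading and on assumed inputs.

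The exercise mechanism does not reach every outcome. In Table 1, FMD and cfPWV have no during-exercise reading. The autonomic outcomes do, but the effect on them was not quantified. For blood pressure, the during-exercise value must come from the finger device, because the cuff is described as used before and after exercise only. If cuff pressure is analysed alone, the mechanism does not arise.

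Finally, the 7% fall in SD is a within-cell figure and should not be read as error bars 7% too narrow. Residual screening also trims some normal values, and the same-day raw-data checks under Data integrity partly cover technical faults, although they set no exclusion rule.

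**Conclusion.** The concern holds in limited form. The stated flagging rule suits a rest-exercise-recovery design poorly because it is not tied to the fitted model, and the plan does not say which run carries the conclusion. The consequence is confined to the trimmed run and whatever is concluded from it.

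Its size depends on how the box plot is drawn. Pooled, the rule mainly removes true during-exercise blood pressure readings and shrinks both the exercise response and any sex difference in it, with the amount set by the assumed SBP values. Per cell, the harm is small: a few per cent of sound data flagged and a slight understatement of residual SD. Severity is minor to moderate. The point rests mainly on the poor fit between rule and design and on a better rule being easy to state; leaving the main run unnamed would, taken alone, be little more than a missing detail.

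**What to change.** In the Statistical analysis section:

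1. State that the model fitted to all data is the reported result for every outcome, and that the trimmed run is a sensitivity analysis only.
2. For that run, replace the box plot of observations with standardised conditional residuals of the fitted mixed model (log scale for HRV) beyond a stated cut-off wide enough to lose few normal values. As an illustration, a cut-off of 3 flags 2(1 − Φ(3)) = 0.27% of normal residuals, about 2 of 750. If spread is larger during exercise, standardise by the SD at each time point, otherwise exercise readings would again be over-flagged.
3. Remove readings from the main analysis only for a documented technical fault, decided without knowledge of training condition. The existing same-day data check is a natural place for this.

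The cost is two or so sentences in the SAP and trivial code. The remaining drawback is that any residual cut-off still flags a small share of normal values, which is acceptable in a run labelled as sensitivity only.

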#### Study main outcomes

The main outcomes of this study are brachial BP (i.e., SBP and DBP), cardiac autonomic function (i.e., RMSSD, HF, and cardiac baroreflex sensitivity), and vascular function (i.e., flow-mediated dilation (FMD), and central pulse wave velocity (cfPWV)).

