**Arterial stiffness:** cfPWV the non-invasive gold standard measurement of central arterial stiffness will be assessed using an applanation tonometry automatic device (NIHem, Cardiovascular Engineering Inc) with participants lying supine. Briefly, common carotid artery and femoral artery pressure waveforms will be recorded using a high-fidelity strain-gauge transducer placed separately on both arteries permitting pulse transit time estimation through the ECG R-wave to the foot of the applanation waves (intersecting tangent foot-to-foot method). PWV is then calculated by dividing carotid-femoral distance (subtraction method) by pulse transit time (26). Pulse waveforms velocity from carotid-brachial and radial artery tracts will also be measured and interpreted as regional indices of upper limb stiffness. All measurements will be conducted by reliable operators (i.e., CVs < 5%) on the right side of the body and ensuring that repeated measurements differ by less than < 0.5 m.s (27). Brachial waveforms and BP will be used to calibrate central pressure waveforms.

Local carotid stiffness and blood flow will also be measured from the common carotid artery using a high-resolution ultrasound (Arietta 750, Fujifilm, Tokyo, Japan) and high frequency (7.5 MHz) linear probe. Carotid artery diameter and blood velocity will be measured using the wave intensity mode with the probe placed on the skin over the carotid artery approximately 1-2 cm to the proximal carotid bifurcation with a 60-degree insonation angle. Carotid stiffness indices such as  $\beta$  stiffness (eq.1) and PWV (eq.2) will be estimated according to the manufacturer's formulas:

$$(eq. 1) \beta = \ln \left[ \frac{SBP/DBP}{(D_{syst} - D_{diast})/D_{diast}} \right]$$

Where,  $\beta$  is beta stiffness; SBP, brachial systolic blood pressure, DBP, diastolic blood pressure;  $D_{syst}$ , brachial artery diameter during systole;  $D_{diast}$ , brachial artery diameter during diastole.

$$(eq. 2) PWV = \sqrt{((\beta \times DBP)/(2\rho))}$$

Where, PWV is brachial artery pulse wave velocity;  $\beta$ , beta stiffness, DBP, brachial diastolic blood pressure; and  $\rho$ , is blood density - assumed constant (1050 kg/m^3).

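### cfPWV is read as arterial stiffness, but its model has no term for the pressure at which it is taken, so part or all of a cfPWV effect may reflect a blood pressure difference

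*Combined protocol and SAP*

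**What the plan says.** All references are to the combined protocol and SAP.

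- **Role of cfPWV.** Study main outcomes lists it under "vascular function (i.e., flow-mediated dilation (FMD), and central pulse wave velocity (cfPWV". The Vascular function section introduces it thus: "cfPWV the non-invasive gold standard measurement of central arterial stiffness will be assessed".
- **How it is computed.** "PWV is then calculated by dividing carotid-femoral distance (subtraction method) by pulse transit time". No pressure normalisation follows. Brachial pressure is used there to calibrate the central pressure waveforms, not to correct cfPWV.
- **How it is modelled.** Statistical analysis states: "Fixed effects will be set as time, sex, training condition, and the random intercept as each participant". It continues: "MVC, %fat and free fat mass, and physical activity outcomes will be added to all linear mixed models as covariates". FMD and HRV each receive one further outcome-specific covariate. cfPWV receives none.
- **Pressure data.** Table 1 puts BP and arterial stiffness in the same 5-minute block at rest and at 5, 30 and 60 minutes after exercise. In the Blood pressure section, "Mean arterial pressure will be estimated as" introduces the usual formula: two thirds DBP plus one third SBP.
- **Nearby analyses.** Statistical analysis also plans a repeated measures correlation of BP with the vascular outcomes. Vascular function adds a local carotid beta index (eq. 1) and a local PWV (eq. 2).

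**The concern.** Pulse wave velocity rises with distending pressure even when the wall properties are unchanged. Eq. 2 shows this for the local index: at fixed beta, PWV goes with the square root of DBP. In this trial pressure is meant to move. SBP drives the sample size, the exploratory responder analysis looks for a hypotensive effect of training, and the post-exercise time points are chosen to follow the pressure response.

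The design does not remove the problem. If training lowers pressure, the pressure difference is part of the training-control contrast. Sex is not randomised, so a male-female difference in pressure enters the sex term directly. The trial could then present one blood pressure effect as two findings: lower pressure and better vascular function.

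**Working it through.** **The plan's own figures.** The plan gives no target difference, variance or power for cfPWV, so there is no cfPWV figure to reproduce. The relevant stated figure is the 5 mmHg in Sample size, which is a difference in SBP. The total of 50 is recovered only approximately: with effect size 0.160, two sexes and an assumed six measurements correlated at 0.5, N is 44, and 44/0.85 = 51.8, or 52. Nothing below depends on it, except that 50 x 0.85 = 42.5 suggests about 42 completers.

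**Step 1: from SBP to mean pressure.** MAP = (2/3)DBP + (1/3)SBP. If SBP changes by 5 mmHg and DBP does not, MAP changes by 5/3 = 1.7 mmHg. MAP changes by 5 mmHg only if DBP falls by 5 mmHg as well, which the plan does not state.

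**Step 2: from pressure to PWV.** Eq. 2 is PWV = sqrt(beta x DBP/(2 rho)). With beta and rho fixed, PWV2/PWV1 = sqrt(P2/P1). Three things are assumed, not given: that this local carotid relation carries over to cfPWV with mean or distending pressure as P; operating pressure 75-95 mmHg; PWV 5-8 m/s.

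| Fall in pressure | From 75 mmHg | From 95 mmHg | In m/s |
|---|---|---|---|
| 1.7 mmHg | 1 - sqrt(73.3/75) = 1.1% | 1 - sqrt(93.3/95) = 0.9% | 0.009 x 5 = 0.04 to 0.011 x 8 = 0.09 |
| 5 mmHg | 1 - sqrt(70/75) = 3.4% | 1 - sqrt(90/95) = 2.7% | 0.027 x 5 = 0.13 to 0.034 x 8 = 0.27 |

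For scale, the plan asks that repeat cfPWV readings agree within 0.5 m/s and that operator CV be below 5%.

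**Step 3: could a shift of this size reach significance?** A simplified paired contrast was simulated: 42 completers, no change in intrinsic stiffness and 4000 runs per scenario. Assumed values were cfPWV 6 m/s with CV 5%, baseline pressure 70 or 85 mmHg, between-person SDs of 12% (cfPWV) and 7 mmHg (pressure), and a within-person pressure-change SD of 5 mmHg. The share of runs significant at 0.05 without adjustment was:

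- 1.7 mmHg fall: 14-17% (a repeat with another seed gave 13-16%)
- 3 mmHg fall: 30-42%
- 5 mmHg fall: 70-84%

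At CV 3% the 5 mmHg figure is 96-99%, and at CV 8% it is 38-50%.

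**Step 4: does adjustment help?** With the pressure change as a covariate, measured without error, the rate at CV 5% is 4.5-5.4%, which is nominal. With an assumed MAP error SD of 3 or 5 mmHg per reading (5 mmHg fall, baseline 85 mmHg), it is about 14% and 31%, against 70% unadjusted. Adjustment removes much of the artefact but not all of it.

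**The case against.** **The unadjusted model answers a legitimate question.** It estimates the total effect on cfPWV, and the plan nowhere promises a pressure-independent effect. This stands. The significant results in Step 3 are false only as statements about intrinsic stiffness, so the weakness lies in interpretation and the unadjusted model should stay.

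**The plan does look at pressure and vessels together.** The repeated measures correlation will show whether BP and cfPWV move together, and carotid beta uses SBP and DBP. A reader might infer that the plan ignores the link altogether; it does not. But a correlation gives no pressure-adjusted training, time or sex effect, and carotid beta is a local index outside the main outcomes.

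**The size is easily overstated.** A reader might put the 5 mmHg from Sample size straight into eq. 2 and conclude that the plan's own target difference shifts cfPWV by 3%. The documents do not support that: the 5 mmHg is SBP, it comes from a study of acute exercise, and no training effect on DBP or MAP is given. Eq. 2 also belongs to the ultrasound index, whereas cfPWV is distance over transit time.

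**Adjustment is imperfect.** MAP follows treatment, may mediate the effect and is measured with error. Adjustment also costs power: in the same simulation with error-free MAP, a true 3% stiffness reduction was detected only 49% of the time. This stands, and it argues against using the adjusted result as a gate.

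**Conclusion.** The gap is real. A main outcome interpreted as stiffness has no pressure term in its model, and no other planned analysis supplies a pressure-adjusted cfPWV effect. The artefact is about 1% of PWV (0.04-0.09 m/s) if only SBP moves by 5 mmHg, and about 3% (0.13-0.27 m/s) if distending pressure moves by the full 5 mmHg. Both figures rest on the transferred square-root relation and the assumed pressure and PWV ranges. The significance rates also rest on the simulation inputs and are illustrations, not predictions for the planned mixed model.

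It would go too far to say that a pressure change will be reported as a vascular effect. That requires a real pressure difference, and its detection depends on its size and on cfPWV measurement error. The supported statement is that it can happen and that the plan as written could not separate the two.

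**What to change.** In Statistical analysis, prespecify a companion cfPWV model:

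1. Keep the planned unadjusted model as the total effect.
2. Add a second model with concurrent cuff MAP from the same visit and time point. Preferably split MAP into each participant's mean (between-person) and the deviation from that mean (within-person), because a single MAP term in a random-intercept model mixes the two slopes.
3. Report both side by side, labelled as total and pressure-adjusted effects, with confidence intervals.
4. If the effect shrinks materially after adjustment, describe it as at least partly pressure-dependent. Set no rule that stiffness may be claimed only if the adjusted effect remains significant.

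The cost is one extra model using data already scheduled in Table 1. The limitation should be written into the plan: MAP is post-treatment and measured with error, so the adjusted estimate is supportive and may still contain some pressure effect.
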